2. SYNOPSIS

Title Frequency of HIV diagnoses among people using oral and LA PrEP

Rationale and Background

In the US, out of approximately 1.2 million people who could benefit from pre-exposure prophylaxis (PrEP), it was estimated that approximately 30% had received a PrEP prescription in 2021. Oral PrEP has been shown to be an effective form of HIV prevention. When taken as prescribed, daily oral PrEP reduces the risk of HIV diagnosis by 99% compared to placebo or those who do not use PrEP among men who have sex with men. Tenofovir disoproxil fumarate (TDF)/emtricitabine (FTC) was approved for PrEP on 16JUL2012 and tenofovir alafenamide (TAF)/FTC was approved on 3OCT2019. The effectiveness of oral PrEP depends on the level of adherence to the daily pill regimen. Cabotegravir long-acting injectable (CAB LA) PrEP was approved on 20DEC2021 and has been shown to have superior efficacy compared to daily oral TDF/FTC. The CDC guidelines for PrEP indicate that HIV testing is required before PrEP initiation and recommended every 3 months (oral PrEP) or 2 months (CAB LA PrEP). The guidelines also recommend regular screening for syphilis, gonorrhea and chlamydia for PrEP users. It is important to understand patterns of PrEP use among people who acquire HIV to improve public health and clinical practice. This study will also provide crucial real-world evidence on HIV acquisition on PrEP, PrEP coverage, HIV testing and STI screening in individuals receiving either oral or LA PrEP.

Research Question and Objective(s)

Analyses to meet the study objectives below will be conducted twice during the study period. Analysis #1 will include data from 01JAN2021-31DEC2023 (Obj. 1) and from 21DEC2021-30JUN2024 (Obj. 2-6). Analysis #2 will be a repeat of Analysis #1 with data from 1JAN2021-31DEC2024 (Obj. 1) and from 21DEC2021-30JUN2025 (Obj. 2-6).

1. Estimate the annual incidence of HIV diagnoses among all people without HIV in OPERA
 - a. Among people with an incident HIV diagnosis, characterize history of PrEP use
2. Describe the demographic and clinical characteristics of people who initiate oral and LA PrEP
3. Estimate the frequency and rate of incident HIV diagnoses following index oral PrEP or LA PrEP initiation among people who initiate a PrEP regimen
4. Evaluate PrEP coverage within 12-months following index oral PrEP or LA PrEP initiation among people who initiate a PrEP regimen

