7.3.2. Outcome definitions

People without HIV in OPERA (Obj 1)

Incident HIV diagnosis

- New HIV diagnosis and/or detectable HIV RNA and/or positive antigen/antibody test
- All potential incident HIV diagnoses will be subject to a thorough chart review for confirmation

People with a new HIV diagnosis (Obj 1.a)

Not applicable

Protocol for Non-Interventional Studies PASS Studies and Non-PASS Studies (4.0) March 2024

Template Doc ID: TMF-15706807

Parent Doc ID: VQD-SOP-066694

PrEP users (Obj 2-5)

Incident HIV diagnosis

- Frequency of new HIV diagnosis and/or detectable HIV RNA and/or positive antigen/antibody test
- Months from start of PrEP type (oral vs. LA) to HIV diagnosis
- Rate of incident HIV diagnoses per 100 person-years of follow-up
 - Within the first 12 months after index PrEP start
 - Through study end (Analysis #1: 30JUN2024; Analysis #2: 30JUN2025)
 - Follow-up (FU) will be censored at first of:
 - HIV diagnosis
 - Death
 - Study end (Analysis #1: 30JUN2024; Analysis #2: 30JUN2025)
 - Loss to follow-up (12 months after last clinical contact)
 - 12 months after index date
- All potential HIV acquisitions will be subject to a thorough chart review for confirmation
 - All lab results, diagnoses, ART prescriptions and clinician notes available in OPERA on or after the potential HIV acquisition was identified will be reviewed

PrEP coverage

- Oral PrEP coverage:
 - Proportion of days of access to oral PrEP in the 12-months following index PrEP initiation
 - Follow-up (FU) will be censored at first of:
 - a) Death
 - b) Study end (Analysis #1: 30JUN2024; Analysis #2: 30JUN2025)
 - c) Loss to follow-up (12 months after last clinical contact)
 - d) 12 months after index date
 - Access to oral PrEP will be determined based on the dates and days of supply for each prescription (e.g., a prescription for 30 pills/month with 3 refills provides 90 days of access)
 - a) Each calendar day will only be counted once, even if there is an overlap between access from the prior prescription and start of the next prescription.

$$\% \text{ access} = \frac{\sum \text{Number of pills in each prescription}}{\text{Number of FU days}} \times 100\%$$

- LA PrEP coverage:
 - Proportion of days of coverage by CAB LA over follow-up
 - Follow-up (FU) will be censored at first of:
 - a) Death
 - b) Study end (Analysis #1: 30JUN2024; Analysis #2: 30JUN2025)

- c) Loss to follow-up (12 months after last clinical contact)
- d) 12 months after index date

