Through study end		
HIV diagnosis, n (%)		
Months from start of PrEP type to HIV diagnosis, median (IQR)		
Negative HIV test within 2 weeks before/on start of PrEP type, n (%)		

^a Incident HIV is only counted for the PrEP type used at the time of diagnosis

Table 10 Incidence rate of HIV^a within 12 months of index and through study end among PrEP users

	Oral PrEP N=	CAB LA PrEP N=
Within 12 months of index		
HIV diagnosis, n (%)		
Person-years of follow-up		
IR per 100 py (95% CI)		
Through study end		
HIV diagnosis, n (%)		
Person-years of follow-up		
IR per 100 py (95% CI)		

^a Incident HIV is only counted for the PrEP type used at the time of diagnosis

Table 11. Oral PrEP coverage within 12 months of index among **oral** PrEP users

	Oral PrEP N=
Mean # pills prescribed (SD)	
Median # of pills prescribed (IQR)	
Mean days of follow-up on oral PrEP ^a (SD)	
Median days of follow-up on oral PrEP ^a (IQR)	
Mean % access (total pills prescribed/days of follow-up) (SD)	
Median % access (total pills prescribed/days of follow-up) (IQR)	

^a If index PrEP is oral: shortest of (a) days from index to first CAB LA injection or (b) 12 months after index; if index PrEP is CAB LA injections: shortest of (a) days from start of switch to oral PrEP to study end or (b) 12 months after index

Table 12. CAB LA PrEP coverage within 12 months of index among CAB LA PrEP users

	CAB LA PrEP N=
Mean days covered ^a (SD)	
Median days covered ^a (IQR)	
Mean days of follow-up on CAB LA PrEP ^b (SD)	
Median days of follow-up on CAB LA PrEP ^b (IQR)	
Mean % coverage (days covered/days of follow-up) (SD)	
Median % coverage (days covered/days of follow-up) (IQR)	

^b Total days between injections, up to 37 days between the first 2 injections or up to 67 days between subsequent injections

^a If index PrEP is oral: shortest of (a) days from index to first CAB LA injection or (b) 12 months after index; if index PrEP is CAB LA injections: shortest of (a) days from first CAB LA injection to study end or (b) 12 months after index

Table 13. Incidence rate of HIV testing events within 12 months of index among PrEP users^a

	Oral PrEP N=	CAB LA PrEP N=
Total # HIV testing events within 12 months of index, n		
Person-years of follow-up		
IR per 100 py (95% CI)		

^a HIV testing events are only counted for the PrEP type used at the time of diagnosis

Table 14. Frequency and type of HIV testing among PrEP users^a

	Oral PrEP N=	CAB LA PrEP N=

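### The worked example for oral PrEP access credits 90 days to 30 pills with 3 refills, but a first fill plus 3 refills is 120 days

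*Protocol*

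**What the plan says.** Objective 4 describes PrEP coverage. For oral PrEP, section 7.3.2 defines the measure as "Proportion of days of access to oral PrEP in the 12-months following index PrEP initiation". The basis is given as "Access to oral PrEP will be determined based on the dates and days of supply for each prescription", followed in parentheses by one illustration: "a prescription for 30 pills/month with 3 refills provides 90 days of access". A sub-bullet then says: "Each calendar day will only be counted once, even if there is an overlap between access from the prior prescription and start of the next" one.

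The printed % access formula sums "Number of pills in each prescription" and divides by the number of follow-up days. The shell for Table 11 in Annex 1 does the same, with a row beginning "Mean % access (total pills prescribed/days of follow-up) (SD".

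Oral PrEP is treated as one pill a day; the synopsis says "The effectiveness of oral PrEP depends on the level of adherence to the daily pill regimen". Section 7.9 adds that the EHR holds only prescription records for oral PrEP, so refills have to be turned into days by a rule.

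**The concern.** The illustration is the only place where the protocol shows how refills become days of access. The formula and Table 11 refer to pills but do not say how refills enter the count. Someone writing the derivation would naturally take the example as the specification, and its two halves do not agree: 3 refills on top of a first fill is not 90 days at 30 pills a fill.

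At stake is the numerator of the only oral measure under Objective 4. If the first fill is dropped, a patient with continuous supply who renews when it runs out is recorded as having unsupplied days.

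**Working it through.** **Inputs.** From the section 7.3.2 example: 30 pills per month, 3 refills, 90 days credited. From the synopsis: one pill a day. From section 7.3.2: a 12-month window, taken here as 365 days, with each calendar day counted once. The protocol gives no renewal intervals, so those below are assumed and shown as a range.

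**Reproducing the stated figure.**

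- First fill plus refills: 30 × (1 + 3) = 120 days. This does not give 90.
- Refills only, or three fills in total: 30 × 3 = 90 days. This gives the stated figure, but only by dropping the first fill or by reading 3 refills as 3 fills.

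**Difference for one prescription.** 120 − 90 = 30 days, and 30/120 = 25% of the supply.

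**When the difference shows.** Let the next prescription start on day *s* after the current one. With days counted once, the loss is 0 if *s* ≤ 90, *s* − 90 if *s* is between 90 and 120, and 30 days if *s* ≥ 120 or there is no next prescription (provided follow-up runs that long).

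**Effect on access over 365 days**, for identical prescriptions of 30 pills with 3 refills:

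| Renewal | Days at 90-day credit | Days at 120-day credit | % access, 90 vs 120 |
|---|---|---|---|
| every 90 days | 365 | 365 | 100 vs 100 |
| every 100 days | 335 | 365 | 91.8 vs 100 |
| every 120 days | 275 | 365 | 75.3 vs 100 |
| every 150 days | 245 | 305 | 67.1 vs 83.6 |
| every 180 days | 185 | 245 | 50.7 vs 67.1 |
| none (single prescription) | 90 | 120 | 24.7 vs 32.9 |

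For example, with renewal every 120 days, prescriptions start on days 0, 120, 240 and 360. At a 90-day credit they cover 90 + 90 + 90 + 5 = 275 days, and 275/365 = 75.3%.

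**The formula as printed.** It shows no cap for overlap or for the end of follow-up, despite the count-once rule. With renewal every 90 days, five prescriptions start within the window. Summing pills gives 5 × 90/365 = 123.3% at the example's credit and 5 × 120/365 = 164.4% at 120 pills.

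**The case against.** The best defence is that the 90-day figure is only an illustration. The operative rule is days of supply per prescription, and the formula and Table 11 count pills prescribed, so a careful programmer could reach 120 without the example. The authors may also have meant three monthly fills, in which case 90 days is correct and nothing is biased. Section 5 describes HIV testing every 3 months before oral PrEP is refilled or reissued, which would fit a 90-day supply. If patients renew on that cycle, the table shows no loss even at the 90-day credit.

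Much of this stands. It limits the size and leaves open which number is wrong, but the sentence still needs correcting: either the days or the refill count must change.

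A reader might infer more than the text supports:

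- *That prescriptions without refills get 0 days.* The protocol states no rule of 30 × refills; that extrapolates from one example. Under the days-of-supply rule, 30 pills without refills give 30 days.
- *That false gaps trigger the gap rules.* A 30-day shortfall alone meets neither the 31-day oral gap in the Table 3 footnote nor the 61-day gap in section 7.2.1 and Table 4. It could only lengthen a real break past a threshold, and no passage ties those rules to this example.
- *That the reported oral percentage is biased downward, to the advantage of CAB LA.* The refill error alone can only lower oral access, but the uncapped formula can raise it, so the net direction is open. The protocol calls the study descriptive and specifies no comparison of coverage between the two types.

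**Conclusion.** The point holds as a contradiction in the specification of the oral measure for Objective 4. With refill in its ordinary sense, the example should read 120 days, and 90 conflicts with the pills-prescribed numerator. Programmed as written and counting each day once, it costs up to 30 days per such prescription: 8.2 percentage points of access for a single prescription over 365 days (32.9 − 24.7) and 24.7 points with renewal every 120 days (100 − 75.3). It costs nothing when renewal comes by day 90.

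These sizes rest on three assumptions: that the refill field excludes the first fill, that renewal follows the intervals shown, and that 12 months is 365 days. If three fills in total were meant, only the wording is wrong. It should be settled before the derivation is relied on, because nothing else in the protocol says how refills become days.

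**What to change.** First confirm with the data holder whether the EHR refill field excludes the first fill. If it does, define days of access per prescription in section 7.3.2 as days' supply per fill × (1 + number of refills), and change the example to 120 days. If three fills were intended, keep 90 days and write 30 pills with 2 refills.

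Use the same quantity in the % access formula and in Table 11, and wherever supply end-dates define gaps (the Table 3 footnote and the 61-day entry rule). While the formula is being edited, show the count-once rule in it so that access cannot exceed 100%.

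The cost is a small text edit to the definition, formula and table shell, and a matching change in the derivation program. No new data are needed.

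### The oral PrEP access formula divides pills prescribed by follow-up days, which contradicts the protocol's rule that each calendar day counts once and lets access exceed 100%

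*Protocol*

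**What the plan says.** Section 7.3.2 names the oral measure in words as "Proportion of days of access to oral PrEP in the 12-months following index PrEP initiation". On its basis it says "Access to oral PrEP will be determined based on the dates and days of supply for each prescription", and it adds the counting rule "Each calendar day will only be counted once, even if there is an overlap between access from the prior prescription". The formula printed directly below has as numerator the sum over prescriptions of "Number of pills in each prescription" and as denominator "Number of FU days", times 100%.

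Annex 1 Table 11 carries the pill total into the results. One row is "Mean % access (total pills prescribed/days of follow-up) (SD"), and the median row uses the same ratio. Annex 1 says the shells will be reused for Analysis #2 with only the study periods changed, so both analyses are affected.

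For CAB LA, Section 7.3.2 gives a parallel once-per-day rule. There the formula does apply it: each injection contributes the smaller of its credited days (37 or 67) and the days between injections.

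The two places also end oral follow-up differently. The Section 7.3.2 list has death, study end, loss to follow-up and 12 months after index, but no switch. The Table 11 footnote, for people whose index PrEP is oral, stops at the first CAB LA injection or at 12 months.

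**The concern.** The words describe a quantity bounded at 100%, and the formula has no bound. A programmer cannot follow both. Table 11 repeats the pill total, so the formula is unlikely to be a slip in one equation, and it is what would be reported if the shell is filled as written.

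PrEP coverage is Objective 4, listed among the primary objectives in Section 6. Section 7.7.1.1 describes oral access and CAB LA coverage in the same sentence. As printed, one measure removes overlap and the other does not, so they are not built alike. Means and SDs for oral access could include individual values above 100%, which have no meaning as a proportion of days.

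**Working it through.** The protocol gives no numerical access result, so there is no figure to reproduce. The check applies the printed formula and the written rule to the same prescription histories. These histories are assumed. Their spacing is chosen to resemble the protocol's own setting: its example prescription gives 90 days of access, Section 5 ties reissuing of oral PrEP to three-monthly HIV testing, and Section 7.3.2 sets the on-schedule test window at 76–104 days. One pill is taken as one day of supply, and follow-up is 365 days unless stated.

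Three quantities are compared:
- A, printed formula: total pills / follow-up days.
- B, distinct follow-up days with supply, overlapping supply dropped / follow-up days.
- C, as B, but overlapping supply carried forward and cut at the end of follow-up.

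| History (90-day supplies) | A | B | C |
|---|---|---|---|
| Days 0 and 120 (no overlap, all inside follow-up) | 180/365 = 49.3% | 180/365 = 49.3% | 180/365 = 49.3% |
| Days 0, 76, 152, 228, 304 | 450/365 = 123.3% | 365/365 = 100% | 365/365 = 100% |
| Days 0, 90, 180, 270, 360 (no overlap, last supply runs past day 365) | 450/365 = 123.3% | 365/365 = 100% | 365/365 = 100% |
| Days 0, 60, 120, 300 | 360/365 = 98.6% | 275/365 = 75.3% | 335/365 = 91.8% |
| Day 0 only, follow-up ends on day 60 | 90/60 = 150% | 60/60 = 100% | 60/60 = 100% |

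Spacing of 75 days (starts on days 0, 75, 150, 225, 300) also gives A = 450/365 = 123.3%. Supply then runs without a break to day 390, so the day count is 365/365 = 100%.

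For the fourth row, B is days 0–209 (210 days) plus days 300–364 (65 days) = 275. C is 270 days of continuous supply from day 0, then 65 days from day 300 = 335.

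The third row shows that overlap is not needed: regular 90-day prescribing gives 123.3% because the fifth supply is counted in full although only 5 of its 90 days fall within follow-up.

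The two follow-up definitions also give different answers. For one 90-day prescription and a switch to CAB LA on day 30, the Table 11 footnote gives 90/30 = 300%. The Section 7.3.2 list, which has no switch, gives 90/365 = 24.7%.

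For comparison, take CAB LA injections on days 0 and 30 and then every 60 days to day 330, with the last interval closed at day 365. The LA formula gives 30 + 5 × 60 + 35 = 365, and 365/365 = 100%, with no excess.

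**The case against.** The strongest reply is that the rule stands directly above the formula, so a programmer may apply it, and that the formula is harmless when prescriptions do not overlap and supply ends within follow-up. The first row of the table confirms the second part. The documents give no frequency of overlap or of supply running past follow-up, so the inflation is conditional and its size cannot be stated. The first part does not remove the contradiction, because Table 11 repeats the pill total.

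A second reply is that a pill total simply carries surplus forward, and that pills in hand can cover a later day. That is fair as far as it goes: the protocol does not say that surplus is lost, so a reader who takes the 75.3% in the fourth row as the only correct value goes beyond the text. But carry-forward does not rescue the formula. Supply beyond the end of follow-up is still counted, and 98.6% still exceeds 91.8%.

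Third, early switching is uncommon, so the 300% case is a corner case. Section 7.5 counts 12,110 + 9,740 = 21,850 people whose first formulation was oral. Its 292 later switchers are 1.3% of these; the 767 − 384 = 383 implied by its CAB LA total would be 1.8%. This stands: supply running past month 12 is likely to matter more than switching.

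Finally, the study is descriptive, plans no test of oral against LA coverage, and Section 7.9 already says oral use is known less precisely. That limits the consequence. It does not disclose or excuse a formula that departs from its own definition.

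**Conclusion.** The point holds as a contradiction within the protocol: the oral formula and Table 11 do not measure the proportion of days that Section 7.3.2 defines. With one pill per day of supply, the printed value is never below the day count. It equals the day count when supplies neither overlap nor outlast follow-up. Otherwise it is at or above the day count and can exceed 100%: 123% against 100% under regular 90-day prescribing, and 98.6% against 75.3% or 91.8% with early renewals followed by a gap. These sizes rest on assumed histories, and the effect on the reported mean or median is unknown.

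A reader might infer that oral access is overstated while CAB LA coverage is understated, so that the pair is tilted in oral PrEP's favour from both sides. The documents do not support the second half. The LA formula is capped, but each injection is also credited with a 7-day window, and no net downward bias has been shown.

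The worked example, "a prescription for 30 pills/month with 3 refills provides 90 days of access", is a separate and lesser matter. If the refills follow a first fill there are four fills, 4 × 30 = 120 days; if three fills are meant in all, 3 × 30 = 90. This is an ambiguity of wording. If four fills were meant, counting 90 would lower access, so it adds nothing to the upward effect above.

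**What to change.** - In Section 7.3.2, make the numerator the number of distinct calendar days with oral supply within oral follow-up, divided by days of oral follow-up. This is bounded at 100%.
- State whether overlapping supply is dropped or carried forward. The protocol leaves this open, and in the fourth history it moves the answer from 75.3% to 91.8%.
- Change the Table 11 mean and median access rows to days with access over days of follow-up. The rows for pills prescribed can stay as plain descriptives.
- Align the Section 7.3.2 censoring list with the Table 11 follow-up footnote, so that both treat a switch to CAB LA, death and loss to follow-up the same way.
- Clarify whether the three refills in the example mean three fills in all (90 days) or four (120 days), and program the same rule.

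The cost is one formula, one sentence on overlap, one example, two table rows and one footnote. The prescription dates and days of supply on which Section 7.3.2 already bases access are sufficient, so no new data are needed. Reported oral access may be somewhat lower than under the printed formula.
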